7. TRIAL MATERIALS

Not applicable.

7.1. Trial Product (s)

Not applicable.

7.2. Storage and Drug Accountability

Not applicable.

8. TREATMENT

8.1. Rationale for Selection of Dose

This is a standard observational cohort, and no treatment will be given to the participants from the research team. All participants will be under the standard care under NUH clinics and treated routinely if they are diagnosed with any pregnancy complications such as gestational diabetes mellitus or hypertensive disorder during pregnancy.

8.2. Study Drug Formulations

Not applicable.

8.3. Study Drug Administration

Not applicable.

8.4. Specific Restrictions / Requirements

Not applicable.

8.5. Blinding

Not applicable.

8.6. Concomitant therapy

Not applicable.

9. SAFETY MEASUREMENTS

9.1. Definitions

Define terms e.g. what would be regarded as UPIRTSO events, Serious adverse events etc..

Include details of the protocol specific reporting, procedures, including the individual responsible for each step (e.g. the Investigator, the medical monitor, etc.), how decisions will be made regarding determining relatedness and grading severity, how reports will be distributed and what follow up are required. Include specific details of reporting procedures for:

- Deaths and life threatening events
- other SAEs
- Other adverse events

9.2. Collecting, Recording and Reporting of "Unanticipated Problems Involving Risk to Subjects or Others" – UPIRTSO events to the NHG Domain Specific Review Boards (DSRB)

UPIRTSO events refers to problems, in general, to include any incident, experience, or outcome (including adverse events) that meets ALL of the following criteria:

1. Unexpected

In terms of nature, severity or frequency of the problem as described in the study documentation (eg: Protocol, Consent documents etc.).

2. Related or possibly related to participation in the research

Possibly related means there is a reasonable possibility that the problem may have been caused by the procedures involved in the research; and

3. Risk of harm

Suggests that the research places participants or others at a greater risk of harm (including physical, psychological, economic, or social harm) than was previously known or recognized.

Reporting Timeline for UPIRTSO Events to the NHG DSRB.

1. Urgent Reporting: All problems involving local deaths, whether related or not, should be reported immediately – within 24 hours after first knowledge by the NHG investigator.

2. Expedited Reporting: All other problems must be reported as soon as possible but not later than 7 calendar days after first knowledge by the NHG investigator.

9.3. Collecting, Recording and Reporting of Serious Adverse Events (SAEs) to the Health Science Authority (HSA)

1. For Industry sponsored Trials

All SAEs will be reported to HSA according to the HSA Guidance for Industry “Safety Reporting Requirements for Clinical Drug Trials.”

2. For Principal Investigator initiated Trials

All SAEs that are unexpected and related to the study drug must be reported to HSA.

“A serious adverse event or serious adverse drug reaction is any untoward medical occurrence at any dose that:

- Results in death.
- Is life-threatening (immediate risk of death).
- Requires inpatient hospitalization or prolongation of existing hospitalization.
- Results in persistent or significant disability/incapacity.
- Results in congenital anomaly/birth defect.
- Is a Medically important event.

Medical and scientific judgment should be exercised in determining whether an event is an important medical event. An important medical event may not be immediately life threatening and/or result in death or hospitalization. However, if it is determined that the event may jeopardize the subject and/or may require intervention to prevent one of the other adverse event outcomes, the important medical event should be reported as serious.”

All SAEs that are unexpected and related to the study drug will be reported. The investigator is responsible for informing HSA no later than 15 calendar days after first knowledge that the case qualifies for expedited reporting. Follow-information will be actively sought and submitted as it becomes available. For fatal or life-threatening cases, HSA will be notified as soon as possible but no later than 7 calendar days after first knowledge that a case qualifies, followed by a complete report within 8 additional calendar days.

9.4. Safety Monitoring Plan

There will not be potential risk in the studied participants in this research.

9.5. Complaint Handling –

All complaints will be recorded by the ground staff and reported to the PI. Also, all participants can contact the PI directly with her contact listed in the consent form. The research PI will look into the issue being complained and try all means to solve it. All complains will be addressed and feedback will be given back to the participant.

10. DATA ANALYSIS

10.1. Data Quality Assurance

Study subjects will be identified on all study-related CRFs and databases only by the study ID number, which will

not include any personal identifying information. Collected data will be reviewed intermittently by PI and Co-PI to assure the accuracy of the data.

10.2. Data Entry and Storage

Data will be stored electronically after each subject encountered and will be stored in NUH. A set of de-identifying patients' data related to this study will be stored in NUS work station as well.

11. SAMPLE SIZE AND STATISTICAL METHODS

11.1. Determination of Sample Size

Based on our prior unpublished Asia-Pacific collaborative study on both Chinese and Indians overweight and obese pregnant subjects ($BMI \geq 23 \text{ kg/m}^2$), the effect size based on analysis of variance (ANOVA) for comparison of glucose across five groups will be more than 0.60 (large effect size). Considering a local setting in Singapore that might carry lower effect size in glycemic difference between GDM phenotypes, we are considering a moderate effect size (0.3) for the sample size calculation. As we will be interested in comparing 10 outcomes, the sample size of 200 participants with GDM and overweight/obese will be sufficient to detect a difference of 0.3 effect size across five GDM phenotype with 80% power and 0.5% type-I error (applying Bonferroni correction for 10 multiple comparisons to control type-I error rate to 5%) and 10% drop-out rate. The sample size assumes prevalence of GDM phenotypes at 20% for fasting glucose impairment alone ($n = 40$), 60% for post-challenge glucose abnormality alone ($n = 120$), and 20% for both fasting and post-challenge glucose abnormality ($n = 40$).

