1. BACKGROUND AND RATIONALE

Pregnant women may experience transient hyperglycemia, also known as gestational diabetes mellitus (GDM). GDM increases risks of adverse pregnancy and neonatal outcomes, including pre-eclampsia, macrosomia, preterm birth, and offspring respiratory distress syndrome. The prevalence of GDM varies from 1% to over 30% in different populations and is particularly high (i.e. 2- to 3-fold greater) among pregnant women of Asian descent (i.e. Chinese and Indians) when compared with others (i.e. North American Europeans).

Emerging evidence shows that GDM phenotypic subtypes might have various underlying pathophysiology that could lead to different treatment outcomes. Current guidelines by the International Association of Diabetes and Pregnancy Study Groups (IADPSG) recommend universal screening for GDM among pregnant women during 15-30 weeks of gestation. Since such guidelines define GDM based on any abnormal reading of fasting (≥ 5.1 mmol/L), 1-hr (≥ 10 mmol/L) and/or 2-hr (≥ 8.5 mmol/L) plasma glucose level cut-offs, pregnant women could be categorized into five different glycemic impairment phenotypes, namely: 1) fasting glucose impairment alone; 2) 1-hr post-challenge glucose intolerance alone; 3) 2-hr post-challenge glucose intolerance alone; 4) both 1-hr and 2-hr post-challenge glucose intolerance alone; 5) both fasting and post-challenge glucose abnormality. In a pilot study conducted in NUH, we have discovered that racial and ethnic differences exist in glycemic impairment phenotypes. For example, more than a third of Caucasian women (38%) diagnosed with GDM had fasting glucose impairment alone; while the majority of Singapore Chinese (84%), 2 thirds of Singapore Malay (65%) and more than half of Singapore Indian (57%) women diagnosed with GDM had 1-hr and/or 2-hr post-challenge glucose intolerance alone. In addition, a recent study showed that Indian women developed GDM at lower BMI and had better insulin sensitivity than Scandinavian women. This suggests a potential variation in both insulin sensitivity and fat deposition related β -cell activity across heterogeneous GDM phenotypes, independent of known risk factors of GDM (i.e. maternal BMI, family history of type 2 diabetes (T2D), history of macrosomia and ethnicity).

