11.2. Statistical and Analytical Plans

- a. **Primary outcome analysis:** The primary analysis will be performed on the changes of glycemic profiles, glycemic indexes and targeted metabolites from early to mid-pregnancy (baseline visit and visit 1 in this study) in relation to GDM phenotypes. Time-series analysis and linear regression will be applied for this analytical plan.
- b. **Secondary outcome analysis:** The secondary analysis will be performed on the association between OGTT 0, 1-hr and 2-hr glycemic values (continuous variables) and GDM phenotypes (categorical variables) (as exposure) (visit 1 in this study) with treatment strategies (diet alone, diet and metformin, diet and metformin and/or insulin) received in late pregnancy (as outcomes) (visit 2 in this study). Ordinal logistic regression will be applied for this analytical plan.
- c. **Exploratory outcomes analysis:** In order to build machine learning prediction models, both stepwise logistic regression and ensemble random forest methods will be applied for variable selection. ([name] needs to nourish this).

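### The 80% power claimed for a five-phenotype comparison does not reproduce: 200 women with GDM give 68% to 75%, and the figure of 200 fits three groups

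*Protocol*

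**What the plan says.** Protocol section 1 sets out the classification: "pregnant women could be categorized into five different glycemic impairment phenotypes". Three of the five are forms of post-challenge intolerance (1-hour only, 2-hour only, both time points). The other two are isolated fasting impairment, and fasting plus post-challenge abnormality.

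Section 11.1 takes its effect size from earlier work, as "the effect size based on analysis of variance (ANOVA) for comparison of glucose across five groups", with a value above 0.60. It then steps down for the local setting: "we are considering a moderate effect size (0.3) for the sample size calculation". From this it concludes that 200 women with GDM "will be sufficient to detect a difference of 0.3 effect size across five GDM phenotype with 80% power and 0.5% type-I error". The 0.5% is 5% divided by 10 outcomes, and a 10% drop-out rate is included.

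The following sentence begins "The sample size assumes prevalence of GDM phenotypes at 20% for fasting glucose impairment alone" and gives numbers for three groups only: 40 with isolated fasting impairment, 120 with any isolated post-challenge abnormality, and 40 with both.

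Section 11.2 defines the primary analysis as changes "from early to mid-pregnancy (baseline visit and visit 1 in this study) in relation to GDM phenotypes".

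**The concern.** One short paragraph states the sample size, effect size, number of groups, power, type-I error and drop-out, so the claim can be checked on its own terms. The text says five groups, but the group sizes are given for three. For a fixed total and a fixed f, an omnibus test across more groups has less power, because the same non-centrality is spread over more numerator degrees of freedom. A figure computed for three groups would therefore overstate the power for five.

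The phenotype comparison is the primary aim. If the true effect is near the planned 0.3, a non-significant five-group result would be read against a 20% risk of missing a real difference when the risk is higher.

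**Working it through.** **Inputs, all from section 11.1.** N = 200 women with GDM; f = 0.3; type-I error 0.05/10 = 0.005; target power 80%; drop-out 10%, so 200 × 0.9 = 180 evaluable. The number of groups k is 5 as claimed, or 3 as listed.

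**Assumption.** The 0.3 is Cohen's f with group means weighted by group size. The protocol calls it ANOVA-based and moderate, with 0.60 as large, which fits that scale. Under this definition, power at a given f does not depend on how the women divide among the phenotypes.

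**Formula.** One-way ANOVA F test with k − 1 and N − k degrees of freedom and non-centrality λ = N × f². Power is the probability that a noncentral F variable exceeds the central F critical value at 0.005.

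- N = 180: λ = 180 × 0.09 = 16.2
- N = 200: λ = 200 × 0.09 = 18.0

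**Results at f = 0.3.**

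| Groups | Power, N = 180 | Power, N = 200 | Evaluable N for 80% | Before 10% drop-out |
|---|---|---|---|---|
| 3 | 80.2% | 85.7% | 180 | 180/0.9 = 200 |
| 4 | 73.8% | 80.3% | 200 | 200/0.9 = 222.2, so 223 |
| 5 | 68.2% | 75.4% | 216 | 216/0.9 = 240 |

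**Reproducing the plan's figure.** Only the three-group row returns 200 with every stated input, including drop-out. Four groups return 200 only if drop-out is ignored, and the protocol has no four-group scheme. Five groups fall short even with no drop-out.

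**Effect detectable with 80% power.** Five groups: f = 0.329 at N = 180 and 0.312 at N = 200. Three groups: f = 0.299 at N = 180.

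**Simulation check** (40,000 runs per setting, weighted f = 0.3):

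- Three groups of 36/108/36 under three mean patterns: 80.1% to 80.3%.
- Five groups of 36 under three mean patterns: 68.0% to 68.1%.
- Five unequal groups of 36/18/54/36/36: 68.1%.
- Five groups of 40: 75.1%.

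**Variants at five groups.** Using λ = f² × (N − k) lowers power to 66.4% (N = 180) and 73.8% (N = 200). A type-I error of 0.01 gives 76.0% and 82.0%. It passes 80% only without drop-out, and it contradicts the stated 0.5%.

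**Larger effects, five groups, N = 180.** Power is about 96% at f = 0.40 and above 99.9% at f = 0.60.

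**The case against.** The arithmetic is not in dispute. The arguments on the other side concern its weight and what it shows.

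- **Drop-out may hardly touch the primary analysis.** Phenotype is known only from the visit 1 OGTT, and the primary analysis in 11.2 uses baseline and visit 1. Losses after visit 1 do not reduce it, so 75% may be nearer the truth than 68%. This stands as a reason to quote the range. It does not remove the lower end: baseline or visit 1 data can be missing, and Specific Aim 1 in section 2 runs to late pregnancy.
- **The three-group origin is inferred.** The protocol does not show its calculation, and 200 is a round number. This also stands. The exact match and the three listed groups make the inference strong, but the investigators should confirm it.
- **The definition of f matters.** If f were defined on unweighted means, the non-centrality would depend on which groups differ. For 36/108/36 and f = 0.3, evenly spaced means ordered by group give λ = 72 × 0.135 = 9.72 and about 49% power. If only the middle group differs, λ = 180 × 0.24 × 0.405 = 17.5 and power is about 84%. This stands as a reason to state the definition. It does not support the five-group claim: with five equal groups the two definitions coincide, and with unequal groups no single power exists without a stated split and mean pattern, neither of which 11.1 gives.
- **The consequence is modest.** The earlier estimate exceeded 0.60, the study is observational, and the planned methods are time-series analysis and linear regression, so an ANOVA figure is only a guide. All true. However, the protocol itself chose 0.3 and ANOVA as its planning basis, and on that basis the stated power is wrong.

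**Conclusion.** The concern holds. With f = 0.3 weighted by group size and a 0.5% type-I error, the five-phenotype comparison has 68% to 75% power, which is 5 to 12 percentage points below the stated 80%. The risk of missing a real difference is 25% to 32%, not 20%. Within that range, the applicable value depends on how much of the 10% drop-out falls on the data used in the primary analysis. The 200 is what a three-group calculation gives, and three groups is what 11.1 goes on to size. That this is where the figure came from is a strong inference rather than a documented fact. The error is a misstated planning figure that should be corrected. It is no reason to alter the design, since the detectable effect moves only from 0.30 to between 0.31 and 0.33.

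**What to change.** Have the investigators confirm how many groups the calculation used, then restate 11.1. If three is confirmed, suitable wording would be:

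> *With 200 women with GDM and 10% drop-out (180 evaluable), a one-way ANOVA at 0.5% type-I error has 80% power for f = 0.3 (Cohen's f weighted by group size) across three groups: fasting only, post-challenge only, and both. Across all five phenotypes, power at f = 0.3 is about 68% (75% without drop-out), and 80% power is reached at f of about 0.33 (0.31 without drop-out).*

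The five-phenotype analysis can stay. The alternative, keeping 80% power for five groups at f = 0.3, would need 240 women with GDM before drop-out instead of 200. That is a larger change than the problem warrants.

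The cost is confined to words and figures in 11.1. Recruitment of 800 women and all analyses are unaffected. The only drawback is a less favourable stated power for the five-group comparison.

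### Holm's procedure holds the same 5% error as the Bonferroni rule named in section 11.1 and never rejects less: a minor, free gain in power

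*Protocol*

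**What the plan says.** Protocol section 11.1 explains the type-I error used for sizing by the number of outcomes: "As we will be interested in comparing 10 outcomes". The study is planned for "80% power and 0.5% type-I error" per outcome, the 0.5% coming from "applying Bonferroni correction for 10 multiple comparisons to control type-I error rate to 5" per cent. The effect size is an ANOVA one: "we are considering a moderate effect size (0.3) for the sample size calculation". The stated aim is "to detect a difference of 0.3 effect size across five GDM phenotype", with 200 women with GDM and 10% drop-out. The same paragraph then gives a prevalence split into three groups, 20/60/20 (n = 40, 120 and 40).

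Section 11.2a plans time-series analysis and linear regression for the primary outcome and names no multiplicity procedure. Bonferroni is therefore the only procedure in the protocol. It appears in the sizing paragraph, which does not list the 10 outcomes or call them primary.

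**The concern.** Single-step Bonferroni holds every outcome to 0.5% however many of the others have already been shown to differ. Holm relaxes the threshold as outcomes are rejected and keeps the overall error at 5%. It makes no assumption about correlation and needs only one p-value per outcome, so it fits whatever model section 11.2a leads to.

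The gain is largest when many outcomes truly differ, and Specific Aim 1 in section 2 hypothesises just that: phenotype differences across mean glucose, time in range, variability indices, insulin sensitivity and secretion measures, HbA1c, adipokines and metabolites. If Bonferroni is also the final testing rule, some real differences would go undeclared that Holm would declare from the same women at the same error rate.

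**Working it through.** **Inputs.** From section 11.1: m = 10 outcomes, overall 5%, f = 0.3, one-way ANOVA, 200 women, 10% drop-out, and group number k = 5 (stated phenotypes) or k = 3 (prevalence split). Assumed, because the protocol gives no figure: the number of outcomes that truly differ (1, 3, 5, 8 or 10, each with f = 0.3) and a common correlation between outcomes of 0, 0.5 or 0.8.

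**1. The plan's alpha.** 0.05/10 = 0.005, as stated. With independent outcomes the family-wise error is 1 − (1 − 0.005)^10 = 0.0489, and under any dependence it is at most 10 × 0.005 = 0.05. The correction is valid.

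**2. Power per outcome under Bonferroni.** Evaluable N = 200 × 0.9 = 180. Noncentrality λ = N·f² = 180 × 0.09 = 16.2. Power is the probability that a noncentral F with k − 1 and N − k degrees of freedom exceeds the 0.5% critical value.
- k = 5 (df 4, 175; critical value 3.85): 68.2%.
- k = 3 (df 2, 177; critical value 5.46): 80.3%.

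The plan's 80% with 200 women is thus reproduced with three groups (180/0.9 = 200). With five groups, 80% needs 216 evaluable women, or 216/0.9 = 240 enrolled. Both cases are carried below.

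**3. Why Holm cannot do worse.** Order the p-values and compare them with 0.05/10, 0.05/9, …, 0.05/1, stopping at the first failure.
- Every threshold is at least 0.005, so any outcome with p ≤ 0.005 is rejected by Holm too.
- If m0 nulls are true, the first true null to be rejected is met at step 10 − m0 + 1 at the latest, where the threshold is at most 0.05/m0. The chance that any of the m0 p-values falls that low is at most m0 × 0.05/m0 = 0.05, whatever the correlation.
- The first step is the Bonferroni test itself, so the chance of rejecting anything at all is the same.

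**4. Size of the gain.** Simulation of 10 F tests at 180 evaluable women, all truly different outcomes sharing one pattern of group means. Gain in average power per truly different outcome, in percentage points, at correlation 0 / 0.5 / 0.8:

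| Outcomes that differ | Five groups (from 68%) | Three groups (from 80%) |
|---|---|---|
| 10 | 14.6 / 11.6 / 9.6 | 12.7 / 9.6 / 7.9 |
| 8 | 8.7 / 7.2 / 6.3 | 7.8 / 6.3 / 5.3 |
| 5 | 3.9 / 3.5 / 3.1 | 3.6 / 3.0 / 2.4 |
| 3 | 1.8 / 1.6 / 1.4 | 1.6 / 1.3 / 1.2 |
| 1 | below 0.1 | below 0.1 |

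Correlated settings used 10,000 replicates; repeat runs agree to a few tenths of a point. The ceilings are 68.2% to 82.8% (five groups) and 80.3% to 93.0% (three groups).

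**5. Role of the group-mean pattern.** If each outcome has its own pattern of group means, correlation hardly matters: with five groups and all 10 outcomes differing, the gain is 14.6 / 14.6 / 14.2 points. It falls with correlation only when the outcomes share a pattern, which is plausible for related glucose and insulin measures.

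**6. Error and any-outcome power.** With five groups, eight outcomes differing and correlation 0.5, simulated family-wise error is 1.1% for Bonferroni and 3.8% for Holm. Both are below 5%; Holm uses error that Bonferroni leaves unspent. Power to detect at least one true difference with all 10 differing at correlation 0.5 is 98.0% for both.

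**The case against.** The strongest reply is that Bonferroni in section 11.1 only explains the planning alpha. Section 11.2 does not say how the outcomes will be tested, that procedure is commonly left to the SAP, and a SAP naming Holm would be fully compatible with section 11.1. Bonferroni is also valid, simple and gives direct simultaneous intervals, and sizing at alpha/m is a usual conservative choice even when Holm is used.

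Most of this stands and limits the point. A reader might infer that the protocol tests 10 primary outcomes by single-step Bonferroni; it does not say so. A reader might also infer that the correction is an error, but the level is exact and the control holds. Nor should the absence of a named testing procedure in section 11.2 be held against the protocol. What remains is that the protocol does name one method and gives its purpose as holding the error at 5%, and another method serves that purpose at least as well. Bonferroni intervals can still be reported beside Holm tests, so the argument from intervals does not favour Bonferroni for the tests.

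It is also fair to object that a gain of about 14 points is a best case. It requires all 10 outcomes to differ at f = 0.3 with five groups, and either independence or unrelated phenotype patterns. The protocol does not say how many outcomes should differ by that much, so the figure cannot be read as the expected loss.

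**Conclusion.** The point holds as a minor efficiency gain. Holm dominates the only multiplicity method that the protocol names: same strong 5% control under any dependence, never fewer rejections. At 180 evaluable women the benefit runs from nil (one true difference) through about 3 to 4 points (five) to a ceiling of about 15 points with five groups or 13 with three (all 10). In the least favourable setting, three groups with correlation 0.8, it is 2.4 points with five true differences and 5.3 with eight. These sizes rest on f = 0.3 for every true difference, normal outcomes, and assumed correlations and numbers of true effects.

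A reader might infer that Holm restores the planned 80% for five phenotypes. It does not. With five groups it gets to about 80% or above only if all 10 outcomes differ, and even then it stays at about 77% when the correlation is 0.8 and the pattern is shared; with eight differing it reaches at most about 77%. The five-group aim and the three-group split in section 11.1 are a separate and larger matter and must be reconciled on their own.

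**What to change.** Keep 0.5% in section 11.1 as the conservative planning alpha, so that the sizing does not change on this account. Add one sentence in sections 11.1 and 11.2a: the 10 outcomes will be tested with Holm's step-down procedure at an overall 5%, comparing the ordered p-values with 5%/10, 5%/9 and so on and stopping at the first failure. If simultaneous intervals are wanted, show Bonferroni intervals, noting that an outcome declared different by Holm alone may have a Bonferroni interval that does not exclude no difference.

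The cost is that sentence and slightly less tidy intervals. No additional women, visits or assumptions are needed. The change should be made before outcome data are examined. If the SAP already names Holm, a cross-reference from section 11.1 is enough.
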